The frequency and percentage of patients in each clotting category will be summarized by inspection site (air trap, dialyzer) for each visit including screening visit. The overall score for individual clotting category, which is the highest of the inspection site Air Trap and Dialyzer score, will also be summarized.

In addition, the frequency and percentage of patients for overall score in each clotting category will be summarized by the following visits:

Week 26 or ET results for patients completed Week 8.

The denominator is the number of patients with at least one non-missing clotting assessment for each specific period above. The overall score for individual clotting category (1, 2, 3, or 4) will be analyzed for treatment comparison between each of the ISIS-416858 Treated group and placebo group using the Wilcoxon Rank Sum test.

In addition, the overall score for individual clotting category (1, 2, 3, or 4) will be analyzed using the proportional odds model with treatment as main effect. The proportional odds model with treatment as main effect and baseline clotting category as covariate will also be provided. P-value, odds ratio, and 95% confidence interval will be provided.

At least one clotting category ≥ 3

The frequency and percentage of patients with at least one post-baseline clotting category 3 or greater event after Week 8 (Day 50) and up to last dose + 7 days will be summarized by treatment group for each of the following periods for subjects on treatment:

- Before Week 8
- After Week 8 and up to last dose + 7 days

The denominator is the number of patients with at least one non-missing clotting assessment after Week 8 and up to last dose+ 7 days. The corresponding Ex.act Binomial 95% confidence interval will be provided.

A logistic regression model with treatment as main effect will be used to test the treatment difference between ISIS 416858 versus placebo in the proportion of patients with at least one clotting category 3 or greater. An estimate of the odds ratio, p-value and two-sided 95% confidence interval will be computed from the model using Wald's test. The logistic regression model with treatment as main effect and baseline clotting category as covariate will also be provided.

In addition, the number of events across all subjects of dialysis circuit will be summarized by treatment group.

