Patient percentage of events greater or equal to 3 will be summarized for 2 periods (before Week 8, after Week 8 and up to last dose+ 7 days). The change of the percentages will be summarized and analyzed by ANOVA.

Most severe clotting category

In order to examine the correlation of FXI activity level and clotting, a separate summary on the most severe clotting category will be provided for patients with average Pre-dialysis FXI activity :::{.1}, :::{.2}, :::{.3}, ... , :::{1.0} U/mL during Week 8 and Week 26 (Day 176) (inclusive) for ISIS 416858 treated patients only.

Additional summary for frequency and percent of events with ≥ 3 clotting category with average Pre-dialysis FXI activity :::{0.1}, :::{.2}, :::{.3}, ... , :::{1.0} U/mL during Week 8 and Week 26 (Day 176) (inclusive) will also be provided.

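### SAP 2.4 gives one post-Week-8 denominator for both clotting periods, and the any-event logistic test ignores how many assessments each patient had: a small effect as planned, and cheap to fix

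*Combined protocol and SAP*

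**What the plan says.** SAP 2.4 defines the summary as patients with "at least one post-baseline clotting category 3 or greater event after Week 8 (Day 50) and up to last dose + 7 days". It then lists two reporting periods, one before Week 8 and one "After Week 8 and up to last dose + 7 days". A single denominator follows: "The denominator is the number of patients with at least one non-missing clotting assessment after Week 8 and up to last dose+ 7 days". The block just before it, on individual categories, words its denominator by period: "The denominator is the number of patients with at least one non-missing clotting assessment for each specific period above".

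The test is stated as: "A logistic regression model with treatment as main effect will be used to test the treatment difference between ISIS 416858 versus placebo", comparing the arms "in the proportion of patients with at least one clotting category 3 or greater". No period is named. A second model adds baseline clotting category. Neither model has a term for the number of assessments.

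The same section places clotting analyses in the Per Protocol Population, which SAP 2.1.2 limits to patients missing no more than 2 doses in the first 12 weeks and no more than 5 of 26 overall. It also plans event counts and a per-patient rate: "Patient percentage of events greater or equal to 3 will be summarized for 2 periods", and "The change of the percentages will be summarized and analyzed by ANOVA". SAP 2.1.5 says missing values are generally not imputed.

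**The concern.** There are two separate defects.

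First, the before-Week-8 percentage has a denominator defined by what happens after Week 8, and a lead sentence under which no before-Week-8 event qualifies. A patient assessed only in the early weeks could be counted in the numerator and not in the denominator, or dropped from both. Two programmers could produce different tables from this text.

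Second, the chance of at least one event rises with the number of times a patient is looked at. The window closes with treatment, so stopping early shortens it. A missed assessment has the same effect, because one non-missing assessment is enough to enter the denominator and an unassessed session is in effect scored as no event. If the arms differ in the number of assessments, the odds ratio moves away from 1 with no drug effect, towards less clotting in the arm assessed less.

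**Working it through.** The plan gives no event rate, effect size or power for this analysis, so there is no stated figure to reproduce.

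**Inputs from the documents**
- Clotting visits (SAP 2.1.1, clotting visit-window table): Days 8, 15, 29 and 43 fall before Day 50, which is 4 visits. Days 57, 71, 85, 99, 113, 120, 134, 148, 162 and 176 fall after it, which is 10 visits.
- Doses (protocol 6.1.3): 26 weekly doses, Days 1 to 176. Dose 21 is Day 141.
- Arm sizes (SAP 1.1): 204/3 = 68 per cohort. 68 × 3/4 = 51 per dose, and 3 × 17 = 51 pooled placebo.
- Test: Wald, two-sided 5%.

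**Assumed:** risk p of category 3 or worse per session of 0.05 to 0.20, equal in both arms. Sessions are independent unless noted.

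**Step 1. Number of assessments in the planned population.** Missing the last 5 doses puts the last dose at Day 141. Day 141 + 7 = Day 148, so 8 of the 10 visits remain. Stopping at or before dose 8 means at least 26 − 8 = 18 missed doses, above the limit of 5. On the literal rule, every patient therefore has 8 to 10 scheduled visits after Week 8, and nobody stopped before Week 8.

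**Step 2. Chance of any event, 1 − (1 − p)^m for m sessions**

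| p | m = 8 | m = 10 | Odds ratio, 8 vs 10 |
|---|---|---|---|
| 0.05 | 33.7% | 40.1% | 0.76 |
| 0.10 | 57.0% | 65.1% | 0.71 |
| 0.20 | 83.2% | 89.3% | 0.60 |

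These compare one patient with another, not one arm with another. At p = 0.10, 5 assessments give 41.0% and 1 gives 10.0%. The two reporting periods are not comparable either: 4 visits give 34.4% against 65.1% for 10.

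**Step 3. Arm level, literal rule.** Suppose 20% of one arm has 8 sessions and everyone else has 10. At p = 0.10 that arm has 0.8 × 65.1% + 0.2 × 57.0% = 63.5%, so the odds ratio is (0.635/0.365)/(0.651/0.349) = 0.93. The same calculation gives 0.95 at p = 0.05 and 0.89 at p = 0.20. Simulated rejection with no drug effect (51 vs 51, 40,000 runs):

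| p | All at 10 sessions | 20% of one arm at 8 | 40% of one arm at 8 |
|---|---|---|---|
| 0.05 | 5.4% | 5.5% | 6.1% |
| 0.10 | 4.9% | 5.3% | 6.5% |
| 0.20 | 3.1% | 3.7% | 5.0% |

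**Step 4. If doses after early study termination are not counted as missed.** Protocol 3.4.2 ends the treatment period at Day 176 or early study termination, and SAP 2.1.2 does not say how later doses count. Shortened patients could then have 1 to 8 visits. With 20% and 40% of one arm shortened (sessions drawn evenly from 1 to 8), null rejection is:

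| p | Independent sessions | Strong between-patient variation |
|---|---|---|
| 0.05 | 7.2% to 13.3% | 4.9% to 6.1% |
| 0.10 | 9.8% to 23.8% | 6.0% to 8.7% |
| 0.20 | 12.8% to 35.8% | 6.8% to 12.9% |

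**Step 5. Denominator.** Under the literal rule there are no early leavers to misplace. Hypothetically, take 51 patients assessed early and 20 with an event, with 8 of those 20 leaving before Week 8. The period-specific figure is 20/51 = 39.2%. The stated denominator gives 20/43 = 46.5% if the numerator is left alone, or 12/43 = 27.9% if it is restricted to match.

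**The case against.** The strongest reply is that the chosen population already deals with most of this, and Steps 1 and 3 bear that out. Sessions are also not ignored across the SAP, since the per-patient percentage with ANOVA uses them. That stands, but the ANOVA weights a patient with one assessment the same as one with ten, and it leaves the logistic odds ratio as it is. A common denominator could also be intended for a before/after comparison in the same patients. That is reasonable, but the text does not say so. The preceding block's period wording is limited support, because only one item is listed there.

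Three stronger readings are tempting and are not supported:
- **Bias in favour of the drug.** The protocol names thrombocytopenia and bleeding as potential risks (2.5) and has stopping rules for both (8.6.2, 8.6.3), so earlier stopping on active is conceivable. But no discontinuation rates by arm are given, and more stopping on placebo would reverse the direction.
- **A large distortion from active patients leaving around Day 85.** They would miss 13 of 26 doses, so the literal Per Protocol rule excludes them. Protocol 10.6 and 10.6.4 place pharmacodynamics in the Safety Population, but 10.6 lets clotting use Per Protocol, and the SAP does so.
- **Clotting as the main pharmacodynamic efficacy signal.** The protocol's primary objective refers to FXI activity reduction. The synopsis and note 6 of Appendix A call the clotting measure exploratory.

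What remains is that the Per Protocol rule caps missed doses, not missed clotting assessments.

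**Conclusion.** The point holds as a minor rule that is wrong as written, together with a cheap improvement to the tested analysis. The denominator and lead sentence conflict with the before-Week-8 row on their face, but the numerical effect is near nil in the planned population. Dependence on the number of assessments is real but small under the literal rule: 1 to 3 percentage points between arms when 20% to 40% of one arm is at the minimum, with test size almost unchanged.

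It could matter in two situations. One is that doses after early termination are not counted as missed, where null rejection at 10% per-session risk is about 6% to 24% (4.9% to 35.8% over risks of 5% to 20%). The other is that many assessments are missing, which the documents do not allow to be sized. Notes to file on the Per Protocol set, dated June and September 2019, are listed but not shown and may settle the first.

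All sizes rest on assumed per-session risks and assumed shortened fractions confined to one arm. Visit counts come from the SAP window table.

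**What to change.** 1. Give each period its own denominator. Alternatively, state that the before/after comparison is restricted to patients assessed in both periods, and restrict the numerators to match.
2. Correct the lead sentence so that it covers both periods, and name the period that the logistic model tests.
3. State how doses after early termination count towards the Per Protocol limits.
4. Make the tested comparison, or at least a prespecified sensitivity analysis, a session-level model of category 3 or worse. A logistic GEE, or events out of sessions with robust variance, would serve, with treatment, baseline category and visit. Keep the any-event percentage as a description and report the number of assessments per patient by arm.

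The cost is SAP wording and one model call on data the plan already collects. The downside is that the estimate becomes a per-session odds ratio rather than a per-patient one. The model removes the dependence on the number of sessions. It does not correct for assessments that are missing for reasons related to clotting.

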1.1 Study Overview

This is a Phase 2 multicenter, double-blind, randomized, stratified, placebo-controlled study in end-stage renal disease (ESRD) subjects receiving hemodialysis at least 3 times per week for a minimum of 9 hours per week. Subjects will be stratified based on the diagnosis of documented atrial fibrillation (AF) at Screening (Yes/No), enrolled in PK substudy (Yes/No), enrolled in Platelet substudy (Yes/No), and then subjects will be randomized to 1 of 3 dose cohorts in a 1:1:1 ratio (Cohort A, Cohort B, and Cohort C). Within each dose cohort, subjects will be randomized in a 3:1 ratio to receive treatment with Study Drug (either ISIS 416858 or placebo).

Cohort A: 200 mg ISIS 416858 or placebo SC (3:1)

Cohort B: 250 mg ISIS 416858 or placebo SC (3:1)

Cohort C: 300 mg ISIS 416858 or placebo SC (3:1)

All cohorts will consist of up to 4-week screening period for procedures and a 26-week treatment period followed by a 12-week post-treatment evaluation period.

Approximately 204 subjects are planned to be enrolled in parallel in this study.

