2 ANALYTICAL PLAN

2.1 General Overview of Analyses

2.1.1 General Statistical Methods

Descriptive summary statistics including number of patients, mean, standard deviation, median, and range (minimum, maximum) for continuous variables, and counts and percentages for categorical variables will be used to summarize most data. All statistical tests will be conducted using 2-sided tests with 5% Type I error rate unless otherwise stated.

PK parameters will be summarized using number of patients, mean, standard deviation, coefficient of variation (CV), geometric mean, median, minimum, and maximum.

All analyses and tabulations will be performed using SAS® Version 9.2 or higher and Phoenix/WinNonlin version 6.1 or higher on a PC platform.

A separate analysis for on-treatment period might be provided if deemed necessary.

Pooled groups:

Patients who are placebo-treated will be pooled and analyzed as a single placebo group.

Patients who are ISIS 416858-treated may be pooled and summarized as the ISIS 416858 total group.

Baseline definition:

Unless otherwise specified, baseline for all safety laboratory results will be defined as the last non-missing measurement prior to the first dose. For post-dialysis Blood Urea Nitrogen (BUN) measures for Urea Reduction Ratio (URR) determination, post-dialysis baseline will be defined as the last non-missing post-dialysis measurement prior to the first dose

Analytical visits:

All post-baseline data will be summarized according to the visit windows in the table below. For patients who have multiple visits within a window, the average will be used in the summary for continuous variable and the worst case result will be used for categorical variable.

Table I Visit window for Clotting

Analysis visit	Visit window
Screening	<1
Baseline	last non-missing measurement prior to the first dose
Day8	[2, 11]
Day 15	[12, 21]
Day29	(22, 35]
Day43	[36, 49]
Day 57	[50, 63]
Day71	[64, 77]
Day 85	[78, 91]
Day99	(92, 105]

Day 113	[106, 116)
Day 120	[117, 126)
Day 134	(127, 140)
Day 148	(141, 154)
Day 162	[155, 168)
Day 176	[169, 182]
Day 190	(183, 196]
Day 204	[197, 210]
Day 218	[211, 224]
Day 232	[225, 238]
Day 246	(239, 252]
Day 260	[253, 266]

Table 2 Visit window for Vital Signs

Analysis visit	Visit window
Baseline	last non-missing measurement prior to the first dose
Day 5	(2, 6)
Day 8	[7, 9]
Day 12	[10, 13]
Day 15	[14, 17]
Day 22	[18, 25)
Day 29	[26, 32)
Day 36	[33, 39)
Day 43	[40, 46]
Day 50	[47, 53]
Day 57	[54, 60]

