
[figure not shown]
PROTOCOL SYNOPSIS *Continued*

Treatment Groups	
There will be 3-dose cohorts that will run concurrently. Subjects will be stratified based on the diagnosis of documented atrial fibrillation and then randomized to 1 of 3 dose cohorts in a 1:1:1 ratio (Cohort A, Cohort B, and Cohort C). Within each dose cohort, subjects will be randomized in a 3:1 ratio to receive subcutaneous treatment with either ISIS 416858 or placebo that is added to standard of care hemodialysis therapies as prescribed by their providers, including heparin.
 
Cohort A: Approximately 68 dialysis subjects will be randomized 3:1 to either 200 mg ISIS 416858 or placebo
 
Cohort B: Approximately 68 dialysis subjects will be randomized 3:1 to either 250 mg ISIS 416858 or placebo
 
Cohort C: Approximately 68 dialysis subjects will be randomized 3:1 to either 300 mg ISIS 416858 or placebo

Study Drug Dosage and Administration	
The SC Tolerability assessments using 0.9% sterile saline should be administered as two 0.75 ml noncontiguous injections on Study Days S-14 (\pm 3) and S-7 (\pm 3).
 
For Cohort A, B and C, the Sponsor will provide ISIS 416858 (200 mg/ml, 1.0 ml) and Placebo (1.0 ml). All doses are given by SC injection.
 
Study Drug will be administered SC post-dialysis at any time from when blood is being returned to the subject but must be within 2 hours (preferably within 15 minutes of dialysis conclusion) for a total of 26 consecutive weeks of treatment in all cohorts.
 
The injection volume will be 1.0 ml for Cohort A (200 mg), 1.25 ml for Cohort B (250 mg) and 1.5 ml for Cohort C (300 mg). Cohorts B and C will be administered Study Drug (ISIS 416858 or placebo) as 2 noncontiguous SC injections.

Rationale for Dose and Schedule Selection	Based on the PK/PD profile of ISIS 416858 in the previous Phase 1 (ISIS 416858-CS1) and Phase 2 (ISIS 416858-CS3 and ISIS 416858-CS4) studies, doses up to 300 mg of ISIS 416858 have demonstrated significant reduction in FXI activity and consequent anti-thrombotic effects without an increased bleeding risk.

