In summary, while the number of patients with chronic renal disease on hemodialysis keeps growing, anticoagulation treatment options to prevent the sequelae of ESRD remain limited. Traditional therapies such as warfarin and aspirin have limited efficacy, perhaps in part due to the mechanisms for thrombosis in ESRD, and expose patients to undue bleeding risk. Therefore, a therapy like ISIS 416858 that is being developed to provide anticoagulation without increased risk of bleeding could effectively reduce thrombosis which may positively affect the morbidity and mortality in these high-risk patients. Initial data demonstrating that treatment with ISIS 416858 for 12 weeks reduced FXI activity levels up to 80% without any increase in clinically-relevant non-major or major bleeding support this notion. The development of ISIS 416858 will ultimately determine whether the need for heparin during the dialysis procedure could be reduced or eliminated which could reduce the risk of major hemorrhage and improve the dialysis procedure. This concept is supported by a report in the literature of a dialysis patient with severe congenital FXI deficiency (less than 3% of normal) who received hemodialysis for several months without heparin or any other anticoagulant and did not exhibit clotting in the extracorporeal circuit or any bleeding complications (Takamizawa et al. 2014). Results from an initial study in 43 ESRD subjects on hemodialysis (ISIS 416858-CS4) indicated that ISIS 416858 significantly reduced the incidence of severe clotting events in the dialyzer circuit at doses of 200 mg and 300 mg per week without increased major or Clinically-Relevant Non-Major Bleeding (CRNMB), providing further support to this finding.

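### SAP 2.4 rests the any-severe-clot comparison on Wald's test with no fallback, so it gives no usable result if an arm has no category 3 or higher clot

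*Combined protocol and SAP*

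**What the plan says.** In SAP 2.4, under the analysis of patients with at least one clot of category 3 or higher, a logistic regression with treatment as the only term "will be used to test the treatment difference between ISIS 416858 versus placebo in the proportion of patients" who have such a clot. For this model the odds ratio, the p-value and a "two-sided 95% confidence interval will be computed from the model using Wald's test". The next sentence adds a second model: "The logistic regression model with treatment as main effect and baseline clotting category as covariate will also be provided". It names no test of its own.

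The section gives no exact, score, likelihood-ratio or penalised alternative, and no rule for an empty cell or a fit that does not converge. The exact binomial interval that it plans applies to the percentage within each group, not to the comparison between groups.

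The general rule in SAP 2.1.1 applies: "All statistical tests will be conducted using 2-sided tests with 5% Type I error rate unless otherwise stated". For group sizes, SAP 1.1 states that "Approximately 204 subjects are planned to be enrolled in parallel in this study". The protocol synopsis (Treatment Groups) puts about 68 in each cohort, randomised 3:1, and SAP 2.1.1 adds that "Patients who are placebo-treated will be pooled and analyzed as a single placebo group". SAP 2.4 runs the clotting analysis on the Per Protocol Population.

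**The concern.** A Wald test divides the estimated log odds ratio by its standard error. When an arm has no events the estimate runs off to infinity, and its standard error grows faster still, so the statistic goes to zero and the p-value towards 1. The clearest possible separation between the arms then prints as no evidence of a difference.

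The expected effect points towards this case. Protocol 2.2 reports that in the earlier dialysis study "ISIS 416858 significantly reduced the incidence of severe clotting events in the dialyzer circuit". A dose arm of about 51, fewer after per-protocol exclusions, could end with very few severe clots or none. The planned p-value, odds ratio and interval would then be unusable, and a replacement would have to be chosen after the data had been seen.

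**Working it through.** **Inputs from the documents.** 204/3 = 68 per cohort. At 3:1 that is 51 active and 17 placebo, so each dose arm has 51 and pooled placebo has 3 × 17 = 51. The test is two-sided at 5%. SAP 2.1.3 and protocol 10.2 give no statistical rationale for the sample size. No power, effect size or category 3 rate is stated, so there is no figure of the plan's own to reproduce.

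**Assumptions.** 45 per arm are analysed (a loss of 6 of 51, about 12%). All event rates are assumed.

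**Method.** With treatment as the only term and events a of n1 (active) and b of n0 (placebo), the Wald statistic is

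z = [ln(a/(n1−a)) − ln(b/(n0−b))] / √(1/a + 1/(n1−a) + 1/b + 1/(n0−b)).

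A zero cell makes this undefined and is counted as no rejection. For two groups, Firth's penalty is equivalent to adding 0.5 to each of the four cells. The penalised likelihood-ratio statistic is twice the difference in log-likelihood of those augmented counts, with and without the treatment term. Power and size are the sums of binomial probabilities over all 2×2 tables with p ≤ 0.05.

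**Empty cell, 0/45 v 8/45.** The Wald p is about 1. For Firth, the log-likelihood with treatment is

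0.5 ln(0.5/46) + 45.5 ln(45.5/46) + 8.5 ln(8.5/46) + 37.5 ln(37.5/46) = −24.77.

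Without treatment it is 9 ln(9/92) + 83 ln(83/92) = −29.47. The statistic is 2 × 4.69 = 9.39, p = 0.002. The odds ratio is (0.5/45.5)/(8.5/37.5) = 0.048. Fisher's exact p is 0.006.

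**Few events, against 9/45 on placebo.** With one active event, z = (ln(1/44) − ln(9/36))/√(1 + 1/44 + 1/9 + 1/36) = −2.398/1.078 = −2.22, p = 0.026.

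| Active events | Wald p | Firth p |
|---|---|---|
| 1/45 | 0.026 | 0.007 |
| 2/45 | 0.039 | 0.026 |
| 3/45 | 0.075 | 0.068 |

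Each pair falls on the same side of 0.05. Borderline tables can differ: 1/45 v 7/45 gives 0.055 and 0.028; 2/45 v 8/45 gives 0.062 and 0.048.

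**Power, 45 v 45.** The chance of no active event is (1−p)^45.

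| Placebo v active rate | Wald | Firth | Fisher | Chance of no active event |
|---|---|---|---|---|
| 15% v 2% | 18% | 63% | 45% | 40% |
| 20% v 2% | 38% | 84% | 73% | 40% |
| 20% v 4% | 45% | 68% | 56% | 16% |
| 30% v 5% | 80% | 91% | 86% | 10% |
| 30% v 10% | 65% | 67% | 58% | 1% |
| 40% v 20% | 55% | 55% | 46% | about 0 |

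At the full planned 51 v 51 with 20% v 1%, Wald has 32% and Fisher 88%; the chance of no active event is 0.99^51 = 60%.

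**Where the loss arises.** Given at least one active event, power for Wald and Firth is 63% and 74% (20% v 2%), 53% and 62% (20% v 4%), and 89% and 90% (30% v 5%). In the first case non-empty tables contribute (1 − 0.40) × (74 − 63) = about 7 of the 46 points lost. The other 39 or so come from the empty cell.

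**Type I error, 45 v 45.** At a common rate of 5%, Wald has 0.1% and Firth 4.1%; at 10%, 1.8% and 4.6%. Wald has 4.4% at 20% and 4.9% at 30%.

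**Pooled active, 135 v 45.** Wald and Firth have 90% and 97% (20% v 2%), 87% and 89% (20% v 4%), and 98.5% and 98.7% (30% v 5%).

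**The case against.** Four arguments weigh against the point.

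- **The rates are unknown, and an empty arm may be unlikely.** The outcome is any category 3 or higher clot in about ten assessment windows after Day 50 (Day 57 to Day 176 in SAP Table 1). With an assumed 1% rate per assessment and independence, 1 − 0.99^10 = 9.6% of patients have an event, and the chance that 45 patients have none is about 1%. A 2% rate per patient needs about 0.2% per assessment. This stands. A reader might infer from protocol 2.2 that near-zero clotting is the expected result, but that section reports a direction, with no rate and no target.

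- **With a few events, Wald performs acceptably.** This largely stands. A reader might infer that the test loses most of its power whenever active events are few. The tables do not support that: with 1 to 3 events the loss is small to modest, and Wald is often close to Fisher. Nor is the type I error far below 5% in general, only at common rates of about 10% or lower.

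- **The contrast may be pooled active against placebo.** The logistic sentence speaks of drug versus placebo, whereas the Wilcoxon sentence in the same section specifies each treated group. The text does not settle this. Pooling shrinks the loss but does not remove it.

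- **The consequence is limited.** The synopsis and footnote 6 of Appendix A call clotting exploratory, and protocol 10.6.4 plans a descriptive summary. Counts, percentages and within-group exact intervals would show an arm without events. This lowers the severity. It does not repair the between-group p-value, odds ratio and interval that SAP 2.4 says will be reported. The Wilcoxon and proportional odds analyses concern a different variable, the overall score at Week 26 or early termination.

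**Conclusion.** The point holds in a limited form. Wald inference with no fallback breaks down when an arm has no category 3 or higher clot; that follows from the method and needs no assumed rate. How likely this is, and so how much power is lost, depends on rates that the documents do not give. Under the assumed rates at 45 per arm, the loss against Firth is large when the true active rate is near 1–2%, moderate at 4–5%, and negligible at 10% or more. Most of it comes from the empty cell. The power figures are for the unadjusted model, per dose arm; they are smaller losses if the active arms are pooled. The documents do not support the wider reading that the planned test is weak across all plausible rates. Severity is minor to moderate.

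**What to change.** In SAP 2.4, replace the reference to Wald's test with Firth penalised-likelihood logistic regression, reporting the profile penalised-likelihood 95% confidence interval and the penalised likelihood-ratio p-value. State that this applies to both the unadjusted model and the model adjusted for baseline clotting category, since the latter currently names no test and a sparse baseline category can cause the same failure. In the same sentence, say whether the contrast is each dose arm or pooled active against placebo.

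An ordinary likelihood-ratio test would also cope with an empty cell, but its type I error reaches 8.7% at a common 5% rate with 51 per arm, whereas Firth's was 4.1% at that rate with 45 per arm.

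The cost is one SAP sentence and one software option. When events are common the results are practically unchanged (55% power for both at 40% v 20%).
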